4 STATISTICAL CONSIDERATIONS

4.1 Standard Operating Procedures and Software

Data will be handled and processed per the sponsor representative's (Avance) Standard Operating Procedures (SOPs), which are written based on the principles of Good Clinical Practice (GCP).

All data conversions and statistical analyses will be performed using SAS® Version 9.4 or higher (SAS Institute, Cary, North Carolina, USA) with program code prepared specifically for the study by qualified Avance statisticians and SAS® programmers.

4.2 General Considerations

All data collected during the study (data originating from the electronic Case Report Forms (eCRFs) or electronic transfers will be presented in the data listings. Event-based listings will be sorted by treatment group, participant identifier and event start date/time (i.e., AE start date/time). Assessment-based listings will be sorted by treatment group, parameter name (alphabetically unless specifically stated otherwise), participant identifier, visit and time point (if applicable).

Unless otherwise stated, the following methods will be applied:

- Continuous variables: Descriptive statistics will include the number of non-missing values (n), arithmetic mean, standard deviation, median, minimum and maximum values. The minimum and maximum values will be displayed to the same decimal precision as the source data, the arithmetic mean and median values will be displayed to one more decimal than the source data, and the SD values will be displayed to two more decimals than the source data for the specific variable. The appropriate precision for derived variables will be determined based on the precision of the data on which the derivations are based, and statistics will be presented in accordance with the abovementioned rules.
- Categorical variables: Descriptive statistics will include frequencies and percentages per category. The denominator in all percentage calculations will be the number of participants in the relevant analysis population with non-missing data, unless specifically stated otherwise. Percentages will be rounded to one decimal place and will not be displayed for zero frequencies.
- Presentation of p-values and confidence intervals: 95% confidence intervals will be computed, and reported to four significant figures, p-values will be displayed up to three decimal places and as “<0.001” if the value is below 0.001.
- Repeat/unscheduled assessments: Only values collected at scheduled study visits/time points will be presented in summary tables. If a repeat assessment was performed, the result from the original assessment will be presented as the result at the specific visit/time point. All collected data will be included in the data listings. If an unscheduled visit was intended to replace the missing assessment for a scheduled visit this should be documented clearly before values are carried forward as a scheduled visit assessment.

- Assessment windows: All assessments will be included in the data listings and the protocol specified visit windows will not be applied to exclude assessments that were not performed on the protocol specified visit days. Protocol visit windows will be as per CRF data collection.
- Result display convention: Results will be centre aligned in all summary tables and listings. Participant numbers, visit, and parameter labels and comments may be left aligned if required.
- Date and time display conventions: The following display conventions will be applied in all outputs where dates and/or times are displayed:
 - Date only: DD-MMM-YYYY
 - Date and time: DD-MMM-YYYY/HH:MM

If only partial information is available, unknown components of the date or time will be presented as UN (Unknown), for example “UN-UNK-2020” or “UN:UN” for time.

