# 7 PARTICIPANT SELECTION

The screening period starts with the signing of the informed consent. During the screening period, inclusion/exclusion criteria for the study participation will be checked/tested. Subjects who meet all inclusion criteria and do not meet any exclusion criterion will be eligible to be enrolled. Those who are not eligible for enrollment or dosing will be considered as screening failures. Data for screen failure reason, eligibility criteria, and demography will be captured on the appropriate screening and enrolment log.

Assessments may be repeated once, if abnormal values were recorded in the first instance, at the discretion of the PI. Values outside of the ranges specified in the criteria below may be considered acceptable if determined by the Investigator (in conjunction with the study medical monitor) to be not clinically significant (NCS).

Unless specifically defined below, inclusion and exclusion criteria are to be assessed at screening and again on Day 1, prior to dose administration.

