### **11.10 Clinical Laboratory Assessments**

Blood samples will be collected for haematology, clinical chemistry and coagulation safety assessments; urine samples will be collected for urinalysis, and urine drugs of abuse testing. An alcohol breath test will be performed as indicated in the schedule of assessment for each study part.

Tests performed by the local laboratory are described in [Appendix 5](#). All abnormal assessments assessed as clinically significant (CS) by the PI will be repeated. Abnormal assessments that are not CS may be repeated at discretion of the PI. Note: Any deviation in laboratory values that are confirmed on re-examination to be CS and (in the opinion of the PI or medically qualified nominee) would jeopardise the safety of the participant or impact on the validity of the study results), will result in exclusion/withdrawal of that participant.

All safety laboratory assessments will be assessed by a certified local laboratory, using that laboratory's normal ranges. The Investigator must review the laboratory report, document this review, and record any CS changes occurring during the study in the AE section of the eCRF.

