### 11.13 Vital Signs

Vital signs assessments will include systolic and diastolic blood pressure, pulse rate, respiratory rate (RR), and oral temperature. Participants should be resting in a supine/semi-supine position for at least 5 minutes prior to and during vital signs measurements.

Vital signs assessments may be repeated once, if abnormal values (outside of site's normal ranges) were recorded in the first instance, at the discretion of the PI (or delegate).

All CS findings post-dose will be recorded as AEs.

Site normal vital signs ranges are as follows:

- Temperature:  $\geq 35.5 \text{ } ^\circ\text{C}$  to  $\leq 37.7 \text{ } ^\circ\text{C}$
- Pulse Rate:  $\geq 45 \text{ bpm}$  to  $\leq 100 \text{ bpm}$
- Respiratory Rate:  $\geq 12$  to  $\leq 22 \text{ breaths/min}$
- Systolic Blood Pressure:  $\geq 90 \text{ mmHg}$  to  $\leq 160 \text{ mmHg}$
- Diastolic Blood Pressure:  $\geq 50 \text{ mmHg}$  to  $\leq 95 \text{ mmHg}$

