### 11.14 Electrocardiogram

12-lead ECG will be performed at Screening, and at End of Study for both study parts. At each protocol scheduled timepoint, ECGs will be performed in triplicate with each replicate separated by at least 1 minute and the full set of triplicates completed within 5 minutes. The mean value for the triplicate will be utilised. Each ECG will be conducted in a supine (or semi-supine) position after the participant has been resting for at least 5 minutes in a quiet setting without distractions (e.g., television, mobile phones).

Site normal ranges for ECG parameters are as follows:

- HR: 45 bpm to 100 bpm
- PR:  $\geq 120 \text{ msec}$  to  $\leq 220 \text{ msec}$
- QRS:  $< 120 \text{ msec}$
- QTcB & QTcF:  $\leq 470 \text{ msec}$  (females) or  $\leq 450 \text{ msec}$  (males)

ECGs will be interpreted, signed, and dated by the PI (or delegate). The ECGs will be classified as normal, abnormal NCS, or abnormal clinically significant. In addition, ECG parameters of ventricular HR, PR interval, QRS duration, QTcB and QTcF will be noted on the eCRF.

Abnormal ECGs that are clinically significant will be repeated. In the case of evident bad quality (e.g., muscle tremor) of the tracing, an ECG will be repeated. Abnormal ECGs that are NCS may be repeated in at the Investigator's discretion. Repeat assessments will be performed in triplicate.

---

Additional ECGs may be performed at any time during the study as required, at the discretion of the PI (or designee).

All CS findings post-dose will be recorded as AEs.

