4.3 Key Definitions

The following definitions will be used:

- Date of the First Study Treatment Administration: The date of the first study treatment administration is defined as the earliest date on which a study treatment was administered.
- Date of the Last Study Treatment Administration: The date of the last study treatment administration is defined as the latest known date on which a study treatment was administered.
- Baseline: The Baseline value is defined as the last available valid, non-missing observation (including repeat and unscheduled assessments) for each Participant prior to first study treatment administration on Day 1.

For ECG triplicates, the baseline is defined as the mean of the last set of triplicates performed prior to first study treatment administration.

For SNOT-22 results, the baseline is defined as the total score (as defined in section XX) of the last SNOT-22 test performed prior to first study treatment administration.

- Change from Baseline: The change from Baseline value is defined as the difference between the result collected/derived at a particular visit and the Baseline value.

The change from Baseline value at each visit will be calculated for all continuous parameters using the following formula:

$$\text{Change from Baseline Value} = \text{Result at specified visit} - \text{Baseline Value}$$

The change from Baseline value will only be calculated if the specific visit result and the Baseline value for the parameter are both available and will be treated as missing otherwise.

- Study Day: The study day of an event is defined as the relative day of the event starting with the date of the first study treatment administration (reference date) as Day 1 (there will be no Day 0).

The study day of events occurring before the first study treatment administration will be calculated as:

Study Day = (Date of Event - Date of First Study Treatment Administration)

For events occurring on or after Day 1, study day will be calculated as:

Study Day = (Date of Event - Date of First Study Treatment Administration) + 1

Study days will only be calculated for events with complete dates and will be undefined for events that are 'Ongoing' at the end of the study.

- Actual Time from First Dose (hours) in PK related outputs is defined as:

$$(\text{Date/Time of PK Sample collection}) - (\text{Date/Start Time of First Dose on Day 1})$$
- Actual Time Deviation (hours) in PK related outputs is defined as:

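### A repeat reading can replace an abnormal baseline but never an abnormal post-dose value, which tilts the shift tables slightly towards worsening and, read literally, keeps a bad End of Study ECG over its valid repeat

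*SAP*

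**What the plan says.** Two SAP rules treat repeats in opposite ways.

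- **Visits (SAP 4.2).** "If a repeat assessment was performed, the result from the original assessment will be presented as the result at the specific visit/time point". Repeats go to the listings only.
- **Baseline (SAP 4.3).** Baseline is the "last available valid, non-missing observation (including repeat and unscheduled assessments) for each Participant prior to first study treatment administration on Day 1". For ECG: "For ECG triplicates, the baseline is defined as the mean of the last set of triplicates performed prior to first study treatment administration".

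The protocol says when repeats happen.

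- **Eligibility (Protocol 7), checked at screening and again on Day 1:** "Assessments may be repeated once, if abnormal values were recorded in the first instance, at the discretion of the PI".
- **Vital signs (Protocol 11.13):** "Vital signs assessments may be repeated once, if abnormal values", again at discretion.
- **Laboratory (Protocol 11.10):** "All abnormal assessments assessed as clinically significant (CS) by the PI will be repeated". Other abnormal results may be repeated at discretion.
- **ECG (Protocol 11.14):** clinically significant abnormal ECGs are repeated, and so are poor tracings: "In the case of evident bad quality (e.g., muscle tremor) of the tracing, an ECG will be repeated".

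SAP 13.2 and 13.3 plan low/normal/high shift tables from baseline for haematology, chemistry, coagulation and vital signs. For ECG (13.4) and urinalysis (13.2) the SAP plans counts of normal, abnormal not clinically significant (NCS) and abnormal clinically significant (CS), but no shift table. SAP 16, which lists changes from the protocol's analysis, does not mention the repeat rule.

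**The concern.** Repeats are not a random sample of readings: apart from bad tracings, they follow an abnormal first value. A second reading in the same person tends to fall back towards that person's usual level. Before dosing, the SAP accepts that second reading as baseline; after dosing, it does not use it. The tables therefore compare a partly cleaned baseline with uncleaned follow-up. The study has no control group in which the same artefact would show, and changes from baseline in vital signs, laboratory values and ECG are primary endpoints (SAP 2.2.1). A reader of the shift tables could take the imbalance for a drug effect.

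The ECG issue is separate. Protocol 11.14 requires a repeat when a tracing is technically poor. The SAP asks for a valid observation only in its baseline definition. After dosing the general rule in 4.2 applies, and it points to the original set. Each participant has one scheduled post-dose ECG, at End of Study, so no other scheduled post-dose ECG can offset a bad one.

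**Working it through.** **Plan figures.** The documents give no repeat frequency, no share of readings outside the limits and no within-person correlation, so the plan has no figure of its own to reproduce here. Its only design figures, the probabilities of seeing at least one SAE, do reproduce (1 − 0.9^35 = 97.5%; 1 − 0.9^30 = 95.8%), but nothing below depends on them.

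**Assumptions.** No drug effect; normally distributed readings; two-sided limits that flag 5% of readings; correlation ρ between any two readings in a person of 0.5 or 0.85; a share q of abnormal baselines repeated, with the repeat taken as baseline whatever its value.

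**Formulas.** Let p, p2 and p3 be the probabilities that one, two and three readings in the same person are all abnormal. Put D = p − p2 (one reading abnormal, another normal) and R = p2 − p3 (two abnormal, a third normal). Under the SAP rule:

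- normal-to-abnormal (N→A) = D + qR
- abnormal-to-normal (A→N) = (1 − q)D + qR
- net imbalance = qD

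With q = 0, or with original values on both sides, both shifts equal D and balance.

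**Inputs by numerical integration.**

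- ρ = 0.5: p = 0.05, p2 = 0.00925, p3 = 0.00320, so D = 0.04075 and R = 0.00605.
- ρ = 0.85: p = 0.05, p2 = 0.02538, p3 = 0.01772, so D = 0.02462 and R = 0.00766.

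**Expected participants per 30 (Part B), per parameter and visit.**

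| ρ | q | N→A | A→N | Ratio | Extra N→A (30qR) |
|---|---|---|---|---|---|
| 0.5 | 0 | 1.22 | 1.22 | 1.0 | 0 |
| 0.5 | 0.25 | 1.27 | 0.96 | 1.3 | 0.05 |
| 0.5 | 0.5 | 1.31 | 0.70 | 1.9 | 0.09 |
| 0.85 | 0 | 0.74 | 0.74 | 1.0 | 0 |
| 0.85 | 0.25 | 0.80 | 0.61 | 1.3 | 0.06 |
| 0.85 | 0.5 | 0.85 | 0.48 | 1.8 | 0.11 |

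Example, ρ = 0.5 and q = 0.5: N→A = 30 × (0.04075 + 0.5 × 0.00605) = 1.31; A→N = 30 × (0.5 × 0.04075 + 0.5 × 0.00605) = 0.70. A simulation of 2,000,000 participants gives the same two values.

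**Where the imbalance comes from.** In that example the net imbalance is 30 × 0.5 × 0.04075 = 0.61. Only 0.09 of it is added N→A shifts; the other 0.52 is A→N shifts that vanish.

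**Mean change.** With symmetric two-sided limits the drift cancels. With a single limit flagging 5% of readings and ρ = 0.5, simulated drift is about 0.025 SD at q = 0.5 and 0.05 SD at q = 1.

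**Which outputs are reached.**

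- *Vital signs:* the Day 1 pre-dose reading is taken within 2 hours (Part A) or 1 hour (Part B) of dosing (Protocol Appendix 3). A repeat before dosing is feasible, and a shift table is planned. This is the main route.
- *Haematology, chemistry, coagulation:* baseline is normally the Day 1 pre-dose sample. In Part B it is drawn within 1 hour of dosing (Protocol Table 21-B, footnote 16). A repeat prompted by its result is unlikely before dosing; that is an inference.
- *ECG and urinalysis:* baseline is the Screening value, where a repeat is feasible. With no shift table, the asymmetry falls on the normal/NCS/CS counts and, for ECG, on change from baseline.

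**Bad ECG tracing.** Protocol 11.14 requires the repeat, SAP 4.2 tabulates the original, and SAP 13.4 makes no exception. SAP 13.4 also takes the worst replicate for the interpretation, which adds to the problem if the poor set is in the database.

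**The case against.** The strongest defence is that each rule is reasonable alone. The last valid pre-dose value is a natural baseline, and keeping the first scheduled value after dosing stops an abnormal safety result from being overwritten by a later normal one. The analyses are descriptive, every original and repeat is listed, the baseline record is flagged, and clinically significant findings are recorded as AEs whatever the tables show. All of this stands, and it limits the consequence. It does not make the two sides of a shift table comparable.

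A reader might infer more than the documents support.

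- *That the rule creates many false worsenings.* If every abnormal baseline were repeated, the ratio would be 7.7 (ρ = 0.5) or 4.2 (ρ = 0.85). But vital-sign repeats are discretionary, and mandatory repeats are confined to clinically significant laboratory results and to clinically significant or poor-quality ECGs. No shift-table parameter follows a repeat-every-abnormal rule. Even then N→A shifts rise only by 30 × 0.00605 = 0.18 or 30 × 0.00766 = 0.23 per 30.
- *That mean change from baseline is materially biased.* With symmetric limits it is not, and the one-sided drift is small.
- *That invalid ECGs will certainly be tabulated.* No passage says that a bad tracing's intervals are entered as the visit result. SAP 4.2 also lets a documented unscheduled assessment stand in for a missing scheduled one, which could apply if the bad tracing is recorded as not done.

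**Conclusion.** The asymmetry is explicit in the SAP and should be corrected, but its effect is modest. With no drug effect, the shift tables lean towards net worsening by a ratio of about 1.3 if a quarter of abnormal baselines are repeated and about 1.8 if half are. Most of the lean is missing improvement: added N→A shifts are about 0.05 to 0.1 per 30 participants per parameter and visit.

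These figures rest on the assumed 5% abnormal rate, the correlations, the repeat shares and equal correlation between all readings. A repeat minutes after the first reading may agree with it more closely than a later visit does, which would make the lean smaller. The direction does not depend on the assumed values: the net imbalance is qD, positive whenever some abnormal baselines are repeated and readings vary within a person.

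The finding applies mainly to vital signs. The effect on Part B haematology, chemistry and coagulation is probably small. The ECG point needs no simulation: followed literally, SAP 4.2 prefers a technically bad End of Study set over the repeat that the protocol requires, provided the bad set is in the eCRF.

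**What to change.** In SAP 4.2 and 4.3, state one rule for every visit, baseline included:

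1. A repeat replaces the original only when the original is documented as technically invalid, for example a poor ECG tracing.
2. Otherwise the original scheduled value is used on both sides, at least for the shift tables and the normal/NCS/CS counts.
3. All repeats are listed.

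If the sponsor prefers to keep the last pre-dose value as baseline, add a shift table that uses original values on both sides.

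The cost is SAP wording and one derivation flag; no new data are needed. There is a small downside: in those tables a valid repeat closer to dosing would no longer serve as baseline. The change also leaves untouched any normal-to-abnormal shifts that arise because eligibility selects participants with normal pre-dose values.

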4.3 Key Definitions

The following definitions will be used:

- Date of the First Study Treatment Administration: The date of the first study treatment administration is defined as the earliest date on which a study treatment was administered.
- Date of the Last Study Treatment Administration: The date of the last study treatment administration is defined as the latest known date on which a study treatment was administered.
- Baseline: The Baseline value is defined as the last available valid, non-missing observation (including repeat and unscheduled assessments) for each Participant prior to first study treatment administration on Day 1.

For ECG triplicates, the baseline is defined as the mean of the last set of triplicates performed prior to first study treatment administration.

For SNOT-22 results, the baseline is defined as the total score (as defined in section XX) of the last SNOT-22 test performed prior to first study treatment administration.

- Change from Baseline: The change from Baseline value is defined as the difference between the result collected/derived at a particular visit and the Baseline value.

The change from Baseline value at each visit will be calculated for all continuous parameters using the following formula:

$$\text{Change from Baseline Value} = \text{Result at specified visit} - \text{Baseline Value}$$

The change from Baseline value will only be calculated if the specific visit result and the Baseline value for the parameter are both available and will be treated as missing otherwise.

- Study Day: The study day of an event is defined as the relative day of the event starting with the date of the first study treatment administration (reference date) as Day 1 (there will be no Day 0).

The study day of events occurring before the first study treatment administration will be calculated as:

Study Day = (Date of Event - Date of First Study Treatment Administration)

For events occurring on or after Day 1, study day will be calculated as:

Study Day = (Date of Event - Date of First Study Treatment Administration) + 1

Study days will only be calculated for events with complete dates and will be undefined for events that are 'Ongoing' at the end of the study.

- Actual Time from First Dose (hours) in PK related outputs is defined as:

$$(\text{Date/Time of PK Sample collection}) - (\text{Date/Start Time of First Dose on Day 1})$$
- Actual Time Deviation (hours) in PK related outputs is defined as:

$$(\text{Actual PK Sample Collection Time Post Dose}) - (\text{Scheduled PK Sample Collection Time Post Dose})$$
- AE Duration: Adverse event duration (in days, to two decimal places), calculated as

$$(\text{Resolution Date} + \text{Resolution Time}) - (\text{Onset Date} + \text{Onset Time})$$

AE duration will only be calculated for events with complete dates/times and will be undefined for events that are 'Ongoing' at the end of the study.
- Any quantitative laboratory parameters that are given as '<xx' or '>xx' in the database will be imputed with the absolute value of the number without the sign (e.g., <2.2 will be imputed as 2.2) for the calculation of the changes from baseline and for the descriptive statistics. In the listings, no imputations will be performed, and all data will be displayed as recorded in the database.
- Laboratory Parameters:

The L/N/H indicator will be derived, where both the lower and upper limit of the reference range was provided, by following derivation:

 - If the result is less than the lower limit of the reference range, the indicator will be set as "Low".
 - If the result is greater than the upper limit of the reference range, the indicator will be set as "High".
 - If the result is greater or equal to the lower limit of the reference range and less or equal to the upper limit of the reference range, the indicator will be set as "Normal".

